- 4. Develop, implement and assess strategies to recruit, train, and integrate peer CHW health coaches within the PCMH model.

The 36-month intervention will be conducted using a staggered entry design across four, overlapping, 12-month waves to account for CHW caseload limits. This study will test a scalable model of peer health coaching to address the millions of patients at risk for DM, using low cost, culturally congruent personnel to promote prevention of DM in PCMH practice. If successful, our study team will work with VA's Central Office and NY City's Health and Hospital Corporation to translate the model for larger scale implementation.

Characteristics of the Research Population

Number of Subjects

All 12 PC teams at VA NY Harbor and all 4 PCMH teams at BH will be eligible to participate. In our VA PROVE study, 51/52 PCPs participated in the intervention, and we expect similar rates in this project. Eligible patients will be identified through the study's pre-DM registry, which will be based on the EMR and Corporate Data Warehouse (CDW) at each site. This methodology builds on our ongoing national, retrospective cohort study of predictors of DM among veterans with pre-DM back to 2008. Based on preliminary analysis of VA NYHHS data from 2010-2012, 62% of veterans enrolled in PC without DM, have had an HbA1c test in the previous two years.

In the intervention group, we anticipate contacting 2,100 randomly selected patients (1,050 at the VA* and 1,050 at BH) to ultimately enroll about 1,100 patients (550 at the VA and 550 at BH). This outreach sample reflects our assumption that 20% of patients will be unreachable and that 60% of those reached will enroll in the study. Another 1,100 patients attributed to control group providers will be randomly selected as the control group, in accordance with the waiver of HIPAA authorization. As detailed below, the control group will not participate in the CHW intervention. The total sample, including the intervention and control groups, will be about 2,200 patients. This amounts to approximately 265 patients (across intervention and control groups) per wave and per clinical site.

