To assess the overall effectiveness of the CHW intervention we will compare cumulative DM incidence rates and time to DM incidence (in addition to other outcomes: weight loss, obesity rate, and health care utilization) between the two study groups, using intention-to-treat and per protocol analyses. Time to DM incidence at 12-month follow-up of the intervention and control arms, aggregated across the 4 study waves, will be compared using Cox proportional hazard regression models. Chi-square analyses will be conducted to compare outcomes between the two groups for categorical variables (e.g. obesity rate, PAM stage) and t-tests will be conducted for continuous outcomes (e.g. weight change, PAM score). We will then conduct (generalized) linear mixed-effects modeling, which will (1) take into account the intra-cluster correlation coefficient (ICC) of patients within providers and teams, (2) analyze repeated measures at several time-points (baseline, midpoint, and post-intervention) simultaneously, (3) include team or patient level baseline covariates easily, if they are found to be unbalanced between two arms, and (4) deal with attrition problems and other missing data automatically. For categorical outcomes, such analyses will be implemented using SAS Proc GLIMMIX, while using SAS Proc MIXED for continuous outcomes.

We will use multilevel survival analysis to determine the effect of the intervention on time to DM, as patients are enrolled in waves and the time to DM incidence may be censored by the end of study. Specifically, we will fit Cox proportional hazard regression models with mixed effects to examine the hazard ratio between two groups, adjusting for important covariates and taking into account the correlation among patients within teams.

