Staff survey data will be used to assess the self-efficacy and collective-efficacy as a team in preventing DM and in working with a CHW coach. We will compare baseline and post-intervention scores on each of the measures. To test the hypothesis that staff assigned to the intervention teams who work closely with a CHW will improve their self and collective efficacy of DM prevention and CHW coaching, we will compare post-intervention scores for these measures across the study arms using linear regression and controlling for baseline scores and adjusting for staff roles, length of time in their role and site. Survey data will also be used to assess PCPs' readiness to work with CHWs for DM prevention. Baseline and post-intervention scores will be compared using Wilcoxon signed-rank tests.

All interviews transcripts (from PCMH and other staff, practice administrators, CHWs, and key informants) and observations of study team meetings and case conferences will be analyzed for common themes by two independent researchers for qualitative analysis. First, two researchers will read the transcripts to identify key domains. Second, the researchers will independently code two of each set of transcripts. They will then meet to develop initial codebooks with code names and meanings. Third, each coder will apply the codebook to the remaining transcripts. Fourth, coders will meet to compare codes and identify patterns and common themes throughout the transcripts. Baseline interviews will be used to guide toolkit refinement and to explore anticipated facilitators and barriers to incorporating CHWs into the PCMH workflow. Mid- and post-intervention interview data will help us to determine key barriers, facilitators and lessons learned from staff, CHWs, and key informants regarding the implementation of CHWs in PC practice.

To assess implementation fidelity, baseline and 6-monthly scores on the coverage, duration, and frequency of CHW-patient contact for BH and VA patients will be compared using ANCOVA. Content of delivery will also be assessed qualitatively based on a sample of CHW-patient contacts. Implementation fidelity will be compared across BH and the VA to examine if differences in organizational setting shape the implementation process.

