Data from the FACETS neighborhood database of social determinants will be conjoined with study data to describe whether contextual factors pertaining to NYC neighborhoods are associated with prediabetes prevalence across neighborhoods. We will use a multilevel statistical model, with patients nested within neighborhoods, to conduct this analysis.

Process Evaluation: To ensure that the intervention was delivered completely and standardized across the sites, CHWs and clinical teams, there will be continuous monitoring of process outcomes and fidelity to the protocol during the CHW intervention. We will maintain standardized protocols for each toolkit strategy and documentation of peer coaching. The CHW Coordinator will conduct quarterly assessments of the interventions, proportion of patients reached and engaged by site and CHW, fidelity to counseling protocols, and the preferred toolkit and contact strategies.

Statistical Power and Sample Size

The primary study outcome for power calculations is the annual hazard rate of incident DM.

To determine sample size, we begin with the total accessible population of about 46,000 primary care patients served at the two sites (BH and VA). Of these we exclude patients with diagnosed DM (25% at VA and 15% at BH) and those over 75 years of age (who are ineligible for this intervention). Of these eligible subjects, we estimated that about 70% will have had the HbA1c test in the last 2 years and that about 40% of these will have had a test result in the prediabetes range.

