While the above inclusion and exclusion criteria return about 9,300 eligible patients, 8,200 at BH and 1,100 at the VA, CHW caseload limitations preclude us from reaching all these eligible patients during the 3-year intervention. Assuming a caseload of 72 patients per fulltime CHW per wave (with 3.5 fulltime equivalent CHWs across both sites and 4 waves), the intervention is projected to enroll a minimum of 1,008 subjects into the intervention group. An equivalent number of subjects will be randomly selected from the Control teams for a total of at least 2,016 study subjects overall. The intervention and control subjects will be split across the two study sites. After assuming that we will not be able to reach about 20% (due to missing or incorrect contact information) unreachable rate, and that about 60% will consent to enroll in the intervention, we will randomly select about double the 1,008 subjects (about 2,100) for potential enrollment into the intervention in order to enroll the minimum of 1,008 intervention subjects needed to have adequate statistical power.

Power: In the pre-DM population we estimate the 3-year DM incidence to be 15% (based on preliminary analysis of a similar VA cohort from 2010-2012). Based on our analyses, with 1,008 patients allocated to each of the intervention and control groups, we anticipate having 80% power ($\alpha = 0.05$) to detect a difference in time-to-event (DM incidence) between the intervention and control group.

To assess measures of implementation fidelity, specifically coverage, duration, and frequency of CHW-patient contact, we will base calculations on all patients enrolled. Since we will use all available study data from the electronic medical records, power and sample size considerations do not apply. We will assess content of CHW-patient contact using qualitative methods, hence power and sample size considerations do not apply.

To examine the variation in prediabetes prevalence across NYC neighborhoods, we will use available data from BH at the start of the study, in approximately 19,000 patients. These patients meet the study's previously stated eligibility criteria, with two modifications: patients must have (1) any HbA1c result in the past 5 years and (2) an address available in the EHR. Data on all enrolled BH patients at the end of the study, an estimated 1,000 patients, will also be used. Since we will use all available study data, power and sample size considerations do not apply.

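### No patient-outcome model commits to a site or wave term, and the mixed models' balance-based covariate rule would leave site out if the planned site split is achieved

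*Combined protocol and SAP*

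**What the plan says.** The section Analysis: Patient Clinical Outcomes and Health Behaviors sets out four layers of analysis.

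- A first Cox comparison at 12 months, in which the two arms, "aggregated across the 4 study waves, will be compared using Cox proportional hazard regression models".
- Chi-square tests and t-tests, which carry no covariates.
- Linear and generalized linear mixed models (SAS MIXED and GLIMMIX) that allow for correlation within providers and teams and will "include team or patient level baseline covariates easily, if they are found to be unbalanced between two arms".
- A mixed-effects Cox model for time to diabetes that allows for correlation within teams. It adjusts for covariates described only as important; none is listed, and no imbalance condition is attached.

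Neither site nor wave is named in any of these. Site is named for the staff survey, under Analysis: Intervention Implementation: that regression is fitted "controlling for baseline scores and adjusting for staff roles, length of time in their role and site".

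Under Number of Subjects, 12 VA teams and 4 Bellevue (BH) teams are eligible, 550 intervention patients are planned at each hospital, and a further 1,100 controls are planned with no site split given. The section adds: "This amounts to approximately 265 patients (across intervention and control groups) per wave and per clinical site". The recruitment section says that staff are randomised as part of their team. It does not say whether this is done within site.

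**The concern.** Site is part of the design. Patients are selected by site and wave, outcomes come from two separate data warehouses, and the referral programmes differ in length (8 weeks at BH, 12 at the VA). The plan itself asks whether organisational setting shapes implementation. A rule that admits a covariate only when the arms differ on it suits chance imbalances. It does not suit a design factor that may predict outcome.

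The rule serves site poorly in both directions. If site is balanced between arms, it stays out, and a VA–BH outcome difference is attributed to random variation between teams although it largely cancels from the arm comparison. The standard error is then too large and power is lost. If site is unbalanced, it is mixed with the arm effect, and whether it is adjusted for depends on a test of the observed data. The mixed-effects Cox model escapes the rule, but leaves the choice of covariates open.

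**Working it through.** **1. The plan's own figures.** The sample size reproduces: 72 × 3.5 × 4 = 1,008 per arm, and 2,100 × 0.8 × 0.6 = 1,008. The power does not. The plan says "we anticipate having 80% power ($\alpha = 0.05$) to detect a difference in time-to-event" "with 1,008 patients allocated to each of the intervention and control groups", and "we estimate the 3-year DM incidence to be 15" per cent, but gives no hazard ratio or ICC. With D = 4(1.96 + 0.84)²/(ln HR)² events, two-sided 5% and no clustering, 80% power implies HR ≈ 0.71 with about 260 events over 3 years. The yearly hazard is −ln(0.85)/3 = 0.0542, so 12-month incidence is about 5.3%, and about 82 events then imply HR ≈ 0.54. The plan therefore offers no effect size or ICC from which the cost of omitting site can be read; both are assumed below.

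**2. Would the balance rule admit site?**

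- If the planned split is achieved: 265 × 4 = 1,060 per site, less 550 intervention patients, leaves about 510 controls at each site. Both arms are then half VA and half BH, chi-square is about 0, and site stays out.
- If it is not: Statistical Power and Sample Size gives only 1,100 eligible VA patients, fewer than 1,050 for intervention outreach plus about 510 controls. Suppose 550 of them belong to intervention teams (assumed). Then 550 × 0.48 = 264 enrol. If BH makes up the other 744 and controls are 504/504, chi-square = 121 (p < 0.001), and site enters.
- If 16 teams were split 8:8 without strata, the four BH teams would divide 2:2 with probability C(4,2)C(12,6)/C(16,8) = 43%, 3:1 with 49%, and 4:0 with 2C(12,4)/C(16,8) = 8%.

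**3. Weight change.** Assumptions: 6:6 VA teams of 84 and 2:2 BH teams of 252 (504 patients per arm per site), outcome SD 1, team ICC 0.01.

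With site fitted:

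- Variance of a VA team mean: 0.01 + 0.99/84 = 0.0218. For a BH team: 0.01 + 0.99/252 = 0.0139.
- Variance of the arm difference within the VA: 2 × 0.0218/6 = 0.00726. Within BH: 2 × 0.0139/2 = 0.0139.
- Combined SE = 1/√(1/0.00726 + 1/0.0139) = 0.069. A 0.2 SD effect on 13 df has about 76% power.

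Without site, at a 0.2 SD site difference:

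- The apparent team variance rises by about 16 × 0.75 × 0.25 × 0.2²/14 = 0.0086, to 0.0186.
- SE ≈ √[2/(6/0.0304 + 2/0.0225)] = 0.084.
- REML simulation gives a mean SE of 0.085 against a true SD of 0.070, about 21% too wide.

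Simulated power for a 0.2 SD effect (approximate, good to a few points):

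| Assumed VA–BH difference | Without site | With site |
|---|---|---|
| 0 | 77% | 77% |
| 0.1 SD | 72% | 76% |
| 0.2 SD | 59% | 77% |
| 0.3 SD | 38% | 75% |

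**4. Diabetes incidence.** Assumptions: HR 0.5, site-stratified allocation, and a team-level analysis of 12-month incidence standing in for the mixed-effects Cox model. Power without → with site:

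| ICC | Equal rates (5.3%) | VA 4.0% / BH 6.6% | VA 3.0% / BH 7.6% |
|---|---|---|---|
| 0 | 80 → 79% | 73 → 84% | 50 → 86% |
| 0.01 | 45 → 45% | 37 → 43% | 25 → 43% |
| 0.03 | 26 → 26% | 21 → 24% | 15 → 22% |

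At ICC 0.01 and 3.0%/7.6% with no true effect, the mean SE without site is 0.0175 against a true SD of 0.0144, and type I error is 1.5%. With site and no further correction, the mean SE is 0.0130 and type I error 6.2%, so part of the apparent gain is liberal.

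**5. Wave.** For wave incidences running from 3% to 7.7%, pooling rather than stratifying changes the SE by 0.3% or less.

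**The case against.** The strongest reply is that the text is less restrictive than it looks. For time to diabetes, the outcome used for power, the mixed-effects Cox model has no imbalance condition, so site could be among its covariates. The clause for the other models describes what they can accommodate and does not expressly bar balanced factors. A reader might infer that the plan can never admit site; the documents do not support that. It remains true that no model commits to site.

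Second, an even split by arm is implied, not stated: 550 per site is given for the intervention arm only, and the VA pool strains it. This stands, and is why the point is put conditionally.

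Third, the loss needs a site difference in outcome. A reader might take "Of these we exclude patients with diagnosed DM (25% at VA and 15% at BH") as evidence of one. Those figures describe patients who are then excluded; they say nothing about incidence or weight change among prediabetic patients. With no site difference nothing is lost.

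Fourth, the allocation odds should not be read as a forecast of failure. A 3:1 split at BH is workable given 8,200 eligible patients there. The plan also speaks of intervention teams at each hospital and of splitting both groups across sites, which points away from 4:0. Equally, the documents do not report a 6:6 and 2:2 allocation; that is an assumption of the calculation.

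**Conclusion.** The point holds as a gap in pre-specification. Site and wave are absent from every patient-outcome model, and the one explicit covariate rule would leave site out if the implied balance is achieved.

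The size is conditional. Under ICC 0.01 and equal patient numbers by site and arm, the loss for a 0.2 SD weight effect runs from nothing at no site difference, through about 4 points at 0.1 SD and 18 at 0.2 SD, to 37 at 0.3 SD. The diabetes scenarios agree in direction. The ICC, the site difference and the effect sizes are all assumed.

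A reader might infer that the trial's intervals are simply wrong, or that false positives are at risk. Neither follows. With site balanced and a team effect fitted, the error is conservative. Nor does omitting wave cost meaningful precision. Its value lies in guarding against drift over calendar time, and against the effect of providers changing arm between waves, which the attrition text allows.

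**What to change.** Pre-specify site as a fixed effect in every MIXED and GLIMMIX patient-outcome model and as a stratum in the mixed-effects Cox model, whatever the balance tests show. Include wave in the same way, chiefly against secular drift and provider movement between arms. Apply a small-sample degrees-of-freedom correction for the 16 teams; with arm and site fitted, 16 − 3 = 13 between-team degrees of freedom remain. State whether teams were randomised within site, and reconcile the implied site split with the 1,100 eligible VA patients.

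The model changes need SAP wording only, since site and wave are known for every patient. The price is one between-team degree of freedom for site, about 0–2 points of power if the sites do not in fact differ. If teams were not randomised within site, wording cannot undo that; adjustment for site then matters more, and the report should say so.

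### Weight change and obesity rate are tested between arms with t-tests and chi-square tests that state no allowance for team clustering and are not labelled descriptive; the mixed models that follow leave their random effects unstated

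*Combined protocol and SAP*

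**What the plan says.** The trial is cluster-randomised (Study Design). Staff are randomised with their team (Method of Subject Identification and Recruitment, and Consent). Number of Subjects lists 12 VA teams and 4 Bellevue teams as eligible, so there are at most 16 clusters.

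Under Analysis: Patient Clinical Outcomes and Health Behaviors, the paragraph on overall effectiveness covers diabetes incidence "in addition to other outcomes: weight loss, obesity rate, and health care utilization". It plans these steps in order:

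- For time to diabetes, the arms "will be compared using Cox proportional hazard regression models". Clustering is not mentioned there.
- For categorical outcomes, with obesity rate as an example, "Chi-square analyses will be conducted to compare outcomes between the two groups for categorical variables".
- For continuous outcomes, "t-tests will be conducted for continuous outcomes (e.g. weight change, PAM score").
- *Then* come (generalised) linear mixed models, which will "take into account the intra-cluster correlation coefficient (ICC) of patients within providers and teams", "analyze repeated measures at several time-points (baseline, midpoint, and post-intervention) simultaneously" and "include team or patient level baseline covariates easily, if they are found to be unbalanced between two arms".

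The next paragraph returns to diabetes: "We will use multilevel survival analysis to determine the effect of the intervention on time to DM". It specifies a mixed-effects Cox model that allows for correlation within teams.

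Three other places bear on the point. Data Analysis and Data Monitoring places weight loss under the primary hypotheses and describes the unit of analysis as patients rolled up to provider. Statistical Power and Sample Size bases power on incident diabetes. The Attrition/missing data text refers once to a primary analysis without saying which one it is.

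**The concern.** A t-test or chi-square test on individual patients treats them as independent. When whole teams are randomised and outcomes correlate within teams, the standard error is too small and so is the p-value. The paragraph presents these tests as between-arm comparisons of effectiveness. Elsewhere the protocol does label analyses by status: baseline summaries are descriptive and subgroup analyses exploratory. The outcome t-tests and chi-square tests have no such label.

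Weight loss and obesity rate are therefore each tested in two ways, and no sentence says which result is reported as the finding. Weight is not peripheral. It is the second numbered aim and sits under the primary hypotheses, although the analysis section groups it with other outcomes. If the simple test were taken as the result, the risk is a false claim of benefit on weight or obesity.

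**Working it through.** **Inputs from the documents.** At most 16 teams (12 VA, 4 Bellevue); 1,008 patients per arm; alpha 0.05. The plan's enrolment figure reproduces: 72 patients × 3.5 full-time CHWs × 4 waves = 1,008 per arm, or 2,016 in total.

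**Assumptions, because the documents give no figure.** ICC from 0.001 to 0.05; 8 teams per arm; two-sided testing. Two team-size patterns set the range:

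- Equal teams: m = 2,016/16 = 126.
- Equal site halves of 1,008: VA teams of 1,008/12 = 84 and Bellevue teams of 1,008/4 = 252. The size-weighted mean is m = (12 × 84² + 4 × 252²)/2,016 = 338,688/2,016 = 168.

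**Step 1: simple tests at patient level.** Design effect DE = 1 + (m − 1) × ICC. Actual error = 2 × [1 − Φ(1.96/√DE)]. For example, at ICC 0.01 and m = 126, DE = 1 + 125 × 0.01 = 2.25, 1.96/1.5 = 1.307, and the error is 0.191.

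| ICC | DE, m = 126 | Error | DE, m = 168 | Error |
|---|---|---|---|---|
| 0.001 | 1.125 | 0.065 | 1.167 | 0.070 |
| 0.005 | 1.625 | 0.124 | 1.835 | 0.148 |
| 0.01 | 2.25 | 0.191 | 2.67 | 0.230 |
| 0.02 | 3.50 | 0.295 | 4.34 | 0.347 |
| 0.05 | 7.25 | 0.467 | 9.35 | 0.522 |

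Null simulations with the 84/252 pattern (20,000 trials per ICC) agree. At ICC 0.001, 0.01 and 0.05 the t-test gave 0.070, 0.230 and 0.524. The chi-square test, with an assumed 40% obesity rate, gave 0.071, 0.231 and 0.522. If only 70% of patients had a follow-up value (assumed; m about 88 or 117), the formula gives about 6%, 15-18% and 40-45%.

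**Step 2: t-test on provider means.** This takes the unit-of-analysis sentence at its word. Assume 3 providers per team and equal teams, so 126/3 = 42 patients per provider and 24 provider means per arm. Simulated error depends on where the correlation lies:

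| Correlation located at | ICC 0.01 | ICC 0.05 |
|---|---|---|
| team only | about 12-13% | about 22% |
| half team, half provider | about 9% | about 13-14% |
| provider only | about 5% | about 5% |

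**Step 3: does naming the mixed model settle it?** The plan has baseline as a repeated measure but does not list the random effects. Take two time points and equal teams. With team and patient intercepts only, both intercepts cancel out of each patient's change, so the model treats changes as independent. Its arm-by-time statistic is then that of the t-test on change. Simulated error (20,000 trials, ICC of change 0.001, 0.01 and 0.05):

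- Team and patient intercepts only: 0.063, 0.189, 0.475.
- Team-by-time effect added, 14 df (16 teams − 2 arms): 0.029, 0.047, 0.049.

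The protection therefore comes from the team-by-time term and the degrees of freedom, and the plan states neither.

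**The case against.** The strongest reply is that the plan already handles clustering. Mixed models covering both outcome types come in the very next sentence. The missing-data strategy is built on them, and similar models are used for secondary outcomes. The primary hypotheses speak of adjusting for baseline, which a chi-square test on follow-up obesity cannot do. All of this points to the mixed models as the intended basis for inference. It stands: a reader might infer that the trial ignores clustering, and the documents do not support that.

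A reader might also infer that the diabetes result is exposed. It is not, because a mixed-effects Cox model is named to determine that effect. Only the earlier Cox sentence, silent on clustering, needs to be tied to it. Patient activation is outside the point too, since control patients are not surveyed and activation is compared between waves.

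The unit-of-analysis sentence would reduce the inflation for weight if it governs the t-test (Step 2). It is not tied to that test, the provider is not the randomised unit, and a chi-square test on obesity rate is naturally a patient-level test. So this reply holds only in part.

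It is also too broad to say that any positive ICC inflates the error. If both arms have the same VA/Bellevue mix, correlation that comes only from site differences does no harm; simulating that case gave about 5% at ICC 0.01 and between 4% and 5% at 0.05. The harm comes from correlation within teams beyond site.

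Finally, one cannot say how often the simple test and the mixed model would disagree. That depends on random effects and degrees of freedom that the plan does not state, and under the intercept-only reading in Step 3 they would agree.

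**Conclusion.** The point holds in a limited form. For weight change and obesity rate, the plan sets out between-arm tests with no stated allowance for clustering and does not mark them as descriptive. Where outcomes correlate within teams beyond a site difference balanced across arms, their p-values are too small.

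The patient-level error rates in Step 1 apply only if those tests were relied on. They are not the trial's expected error rate, because the mixed models probably decide. On provider means, the t-test's error would be about 5-13% at ICC 0.01 and 5-22% at 0.05. All these sizes rest on an assumed ICC, an assumed 8 versus 8 split, and assumed team and provider sizes.

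Confidence is high in the gap in the text and lower in its size. The second half of the point matters as much as the first: saying that the mixed models prevail would not protect weight change unless their team-level terms are also specified.

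**What to change.** 1. Drop the outcome t-tests and chi-square tests, or present them descriptively without p-values.
2. Name the mixed models as the deciding analysis for weight, obesity rate and other outcomes taken from the medical record. Specify a team random effect, a team-by-time effect where baseline is a repeated measure, and a small-cluster degrees-of-freedom method such as Kenward-Roger or between-cluster df.
3. State that the first Cox sentence means the mixed-effects Cox model. Reword the unit of analysis as patients nested in providers within randomised teams.
4. As a separate, minor improvement, replace covariate choice by observed imbalance with a short pre-specified list, for example site, wave and age.

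The cost is wording and a little programming, with no change to data collection. Confidence intervals will be wider, and correctly so.
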